10.7.6. Reporting of SADEs

SADE Reporting to Pfizer Safety

NOTE: There are additional reporting obligations for medical device incidents that are potentially related to SAEs that must fulfill the legal responsibility to notify appropriate regulatory authorities and other entities about certain safety information relating to medical devices being used in clinical studies.

- Any device deficiency that is associated with an SAE must be reported to the sponsor within 24 hours after the investigator determines that the event meets the definition of a device deficiency.
- The sponsor shall review all device deficiencies and determine and document in writing whether they could have led to an SAE. These shall be reported to the regulatory authorities and IRBs/ECs as required by national regulations.

10.8. Appendix 8: ECG Findings of Potential Clinical Concern

ECG Findings That May Qualify as Adverse Events (AEs)

• Marked sinus bradycardia (rate <40 bpm) lasting minutes.• New PR interval prolongation >280 msec.• New prolongation of QTcF to >480 msec (absolute) or by ≥ 60 msec from baseline.• New-onset atrial flutter or fibrillation, with controlled ventricular response rate: ie, rate <120 bpm.• New-onset type I second-degree (Wenckebach) atrioventricular (AV) block of >30 seconds' duration.• Frequent premature ventricular complexes (PVCs), triplets, or short intervals (<30 seconds) of consecutive ventricular complexes.
ECG Findings That May Qualify as Serious Adverse Events (SAEs)

• QTcF prolongation >500 msec.• New ST-T changes suggestive of myocardial ischemia.• New-onset left bundle branch block (QRS >120 msec).• New-onset right bundle branch block (QRS >120 msec).• Symptomatic bradycardia.• Asystole: In awake, symptom-free participants in sinus rhythm, with documented periods of asystole ≥ 3.0 seconds or any escape rate <40 beats per minute (BPM), or with an escape rhythm that is below the AV node; In awake, symptom-free participants with atrial fibrillation and bradycardia with 1 or more pauses of at least 5 seconds or longer; Atrial flutter or fibrillation, with rapid ventricular response rate: rapid = rate >120 bpm.• Sustained supraventricular tachycardia (rate >120 BPM) (“sustained” = short duration with relevant symptoms or lasting >1 minute).

- Ventricular rhythms >30 seconds' duration, including idioventricular rhythm (rate <40 BPM), accelerated idioventricular rhythm (40< x <100), and monomorphic/polymorphic ventricular tachycardia >100 BPM (such as torsades de pointes).
- Type II second-degree (Mobitz II) AV block.
- Complete (third-degree) heart block.

ECG Findings That Qualify as Serious Adverse Events

- Change in pattern suggestive of new myocardial infarction.
- Sustained ventricular tachyarrhythmias (>30 seconds' duration).
- Second- or third-degree AV block requiring pacemaker placement.
- Asystolic pauses requiring pacemaker placement.
- Atrial flutter or fibrillation with rapid ventricular response requiring cardioversion.
- Ventricular fibrillation/flutter.
- At the discretion of the investigator, any arrhythmia classified as an adverse experience.

The enumerated list of major events of potential clinical concern are recommended as "alerts" or notifications from the core ECG laboratory to the investigator and Pfizer study team, and not to be considered as all inclusive of what to be reported as AEs/SAEs.

10.9. Appendix 9: Diagnostic Criteria for Atopic Dermatitis

Per Inclusion Criterion 2, a participant is to have a clinical diagnosis of atopic dermatitis according to the criteria of Hanifin and Rajka.²¹

Hanifin and Rajka's Diagnostic Criteria for Atopic Dermatitis

Must have 3 or more basic features described below:
Pruritus
Typical morphology and distribution: 
• Flexural lichenification in adults• Facial and extensor eruptions in infants and children
Chronic or chronically-relapsing dermatitis
Personal or family history of atopy (asthma, allergic rhinitis, atopic dermatitis)
Must have 3 or more following minor features:
Xerosis
Ichthyosis/palmar hyperlinearity, keratosis pilaris
Immediate (type 1) skin test reaction
Elevated serum Immunoglobulin E (IgE)
Early age of onset
Tendency toward cutaneous infections (esp. staph. aureus and herpes simplex), impaired cell-mediated immunity
Tendency toward non-specific hand or foot dermatitis
Nipple eczema
Cheilitis
Recurrent conjunctivitis
Dennie-Morgan infraorbital fold
Keratoconus
Anterior subcapsular cataracts
Orbital darkening
Facial pallor, facial erythema
Pityriasis alba
Anterior neck folds
Itch when sweating
Intolerance to wool and lipid solvents
Periofollicular accentuation
Food intolerance
Course influenced by environmental and emotional factors
White dermographism, delayed blanch

10.10. Appendix 10: Prohibited Concomitant Medications which may result in Drug-Drug Interaction (DDI)

The prohibited concomitant medications listed below should not be taken with abrocitinib for the period of time listed below.

The Pfizer study team is to be notified of any prohibited medications taken during the study. After consulting with the sponsor, the investigator will make a judgement on the ongoing participation of any participant with prohibited medication use during the study.

This list of drugs prohibited for potential DDI concerns with the study intervention may be revised during the course of the study with written notification from sponsor, to include or exclude specific drugs or drug categories for various reasons (e.g., emerging DDI results for the study intervention, availability of new information in literature on the DDI potential of other drugs).

This is not an all-inclusive list. Site staff should consult with the sponsor or designee with any questions regarding potential DDI.

Drug Category	Drugs	Required Washout Period requirement
CYP2C9 Inhibitors	amiodarone fluconazole fluvoxamine miconazole oxandrolone voriconazole	1 week or 5 half-lives whichever is longer
CYP2C19 Inhibitors	esomeprazole fluconazole fluoxetine fluvoxamine isoniazid moclobemide omeprazole ticlopidine voriconazole	1 week or 5 half-lives whichever is longer
CYP2C9 Inducers	carbamazepine enzalutamide rifampicin	5 half-lives plus 14 days For example, carbamazepine: The average half-life of carbamazepine after repeat dosing is on average 15 hours, so the washout period is calculated as the sum of 5 half-lives (approximately 3 days) and an additional 14 days for a total of 17 days.
CYP2C19 Inducers	enzalutamide rifampicin	5 half-lives plus 14 days

Half-life refers to the half-life of the parent drug and its metabolites, which are inhibitors or inducers. The longest half-life should be used to calculate the period necessary to washout a medication prior to the first dose of study intervention. For example, fluoxetine and its metabolite norfluoxetine are both inhibitors of CYP2C19. The terminal half-life of fluoxetine is up to 6 days. However, norfluoxetine has a longer half-life, up to 16 days. Therefore, the washout period should be calculated based on the 5 times the half-life of norfluoxetine, for a total of approximately 80 days prior to the first dose of study intervention.

Investigators should consult the dupilumab product label for information regarding medication that is prohibited for concomitant use.

Investigators should consult the product label for any other medication used during the study for information regarding medication that is prohibited for concomitant use.

10.11. Appendix 11: Monitoring and Discontinuation Criteria

This appendix documents the monitoring and discontinuation criteria for this study that, in rare instances, may be extenuating circumstances that might mitigate the need for discontinuation that can be discussed with the medical monitor.

Monitoring Criteria

The following laboratory abnormalities require prompt retesting:

- Neutrophil counts <1000 neutrophils/ mm^3 ; confirmed promptly by repeat testing, ideally within 3-5 days;
- Platelet counts $<75,000$ platelets/ mm^3 ; confirmed promptly by repeat testing, ideally within 3-5 days;
- Any single hemoglobin value <9.0 g/dL or one that drops ≥ 2 g/dL below the baseline value and is also below the lower limit of normal; confirmed promptly by repeat testing, ideally within 3-5 days;
- Any single AST and/or ALT elevation >3 times the upper limit of normal regardless of accompanying symptoms or the total Bilirubin should prompt repeat testing. This should also prompt review of [Appendix 6](#) (Liver Safety); additional investigations must be conducted.

Temporary Interruption to Dosing

An investigator can temporarily interrupt oral study intervention for up to a maximum of 28 consecutive days and up to 2 consecutive doses of injectable study intervention for a participant, for safety reasons or while monitoring abnormal laboratory tests if the investigator judges that this is necessary. In the case of study intervention being withheld, all study interventions that the participant is receiving should be withheld (ie, both oral and injected study interventions). The investigator should use their judgement with regard to unscheduled visits/laboratory/clinical assessments required to monitor the participant during this timeframe. If within this timeframe the investigator judges that it is safe to restart dosing, then the participant may restart study intervention. If the investigator judges that it is not safe to restart dosing within this timeframe then the participant must be permanently discontinued from treatment, have an End of Treatment visit and enter the 4-week follow-up period (See Section 10.12.3 for UK country-specific requirements). Doses not taken for the reasons mentioned above do not constitute protocol deviations or medication errors and should not be considered dosing errors but should be noted in the dosing log with the reason for reduced drug consumption clearly described.

Discontinuation Criteria

Participants must be permanently discontinued from treatment if they meet any of the following criteria at any point in the study:

- Participants who have recurrent suicidal ideation and behavior (SIB) during the trial must be discontinued from the study and treated appropriately. If a participant endorses a 4 or 5 on the ideation subscale or any behavioral item of the C-SSRS on two occasions and is confirmed to have active SIB on both occasions by a risk assessment conducted by a qualified MHP, then the participant must be discontinued from the study and treated appropriately.
- Marked prolongation of the QTcF interval to >500 ms or >60 ms change from screening ECG (refer to [Appendix 8](#)).
- Serious infection (refer to definition for Serious Adverse Events in [Section 10.3.2](#)) must result in temporary interruption of study intervention. Study intervention cannot be restarted until the serious infection has resolved, and unless discussed and agreed with the medical monitor. If the participant cannot be restarted on study intervention within 28 days or the infection is not resolved, or there is no agreement received from the medical monitor then the participant must be permanently discontinued.
- Any bleeding event thought to be associated with a platelet count or hemoglobin reduction per the judgement of the investigator (or, if necessary/desired, following discussion with the medical monitor).
- Adverse event, per judgment of the investigator, requiring discontinuation from treatment (or, if necessary/desired, following discussion with the medical monitor).
- Any adverse event or laboratory abnormality, that per the investigator's judgement requires withholding of oral study intervention for >28 consecutive days and > 2 consecutive doses of injectable study intervention.

NOTE: any initial lab value below must be retested within 48 hours.

- Two sequential platelet counts <50,000/mm³. If the participant has a platelet count <25,000/mm³, study intervention should be temporarily withheld pending the confirmatory retest.
- Two sequential neutrophil counts <500/mm³.
- Two sequential lymphocyte counts <500/mm³.
- Two sequential hemoglobin assessments <8.0 g/dL or <30% from baseline value.
- Two sequential increases in serum creatinine that are >50% over the average of screening and baseline values AND an absolute increase in serum creatinine

≥0.5 mg/dL. At the time of study completion or discontinuation, if a participant should exhibit elevations in serum creatinine ≥33% above the average of screening and baseline values, they will be re-tested every 1 to 2 weeks until the serum creatinine elevation is fully reversed to within 10% of the average of screening and baseline values or has stabilized.

- Any of the following:
 - Two sequential AST or ALT elevations >3 times the upper limit of normal with at least one Total Bilirubin value >2 times the upper limit of normal.
 - Two sequential AST or ALT elevations >3 times the upper limit of normal with an abnormal INR.
 - Two sequential AST or ALT elevations >3 times the upper limit of normal accompanied by symptoms consistent with hepatic injury.
 - Two sequential AST or ALT elevations >5 times the upper limit of normal, regardless of Total Bilirubin or accompanying symptoms.

NOTE: Any of the above LFT findings should prompt review of [Appendix 6](#) (Liver Safety) for which additional investigations must be conducted.

Having met Discontinuation Criteria, the participant must be permanently withdrawn from treatment, have their end of treatment visit, and will then enter the 4-week follow-up period (See Section 10.12.3 for UK country-specific instructions).

Additional individual participant safety monitoring, including laboratory testing or unscheduled study visits, in addition to these guidelines is at the discretion of the investigator and dependent on their judgment of safety concerns. Unscheduled laboratory testing through the central laboratory may be obtained at any time during the study to assess such concerns.

If a participant has a clinically significant, treatment emergent, abnormality at the time of withdrawal from the study, the Pfizer medical monitor (or designee) should be notified and every effort should be made to arrange follow-up evaluations at appropriate intervals to document the course of the abnormality. All abnormal laboratory events of clinical significance should be followed until the laboratory values have returned to normal or baseline levels or are deemed clinically stable. Follow-up for abnormal laboratory findings and adverse events by the investigator is required until the event or its sequelae resolve or stabilize at a level acceptable to the investigator, and Pfizer concurs with that assessment.

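### The haemoglobin stopping rule in Protocol Appendix 11 has a percent limb that does not work as written

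*Protocol*

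**What the plan says.** The discontinuation list in Protocol 10.11 (Appendix 11) opens with "Participants must be permanently discontinued from treatment if they meet any of the following criteria at any point in the study". One item is "Two sequential hemoglobin assessments <8.0 g/dL or <30% from baseline value". A note ahead of the laboratory items adds that "any initial lab value below must be retested within 48 hours". The haemoglobin line therefore sets both the stop and the first value that needs the fast retest.

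Other parts of the appendix bear on the reading:

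- The creatinine item in the same list concerns increases that are ">50% over the average of screening and baseline values", so it names both a direction and a reference.
- The Monitoring Criteria ask for a prompt repeat, ideally in 3 to 5 days, for "Any single hemoglobin value <9.0 g/dL or one that drops" by at least 2 g/dL "below the baseline value and is also below the lower limit of normal".
- Dosing may be interrupted temporarily "for safety reasons or while monitoring abnormal laboratory tests if the investigator judges that this is necessary".
- The appendix's opening sentence allows exceptions: "in rare instances, may be extenuating circumstances that might mitigate the need for discontinuation that can be discussed with the medical monitor".

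Protocol 2.3 names haematopoietic effects as a potential risk. Exclusion criterion 20 sets a screening minimum of 10.0 g/dL. SAP 6.6.2 will summarise participants who meet the monitoring and discontinuation criteria, and does not redefine them. Nothing else in either document defines the haemoglobin percent limb.

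**The concern.** The percent limb has no word for a fall, and its inequality points the wrong way for one. It can be read literally as a value below 30% of baseline or as a change of less than 30%. Neither works as a toxicity threshold. A decrease of more than 30% is the natural guess, but the words do not say it.

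This is a mandatory numeric rule that sites apply to individual participants, so an unusable limb has three effects if a decrease of more than 30% was meant:

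- A sustained large fall that stays at or above 8.0 g/dL has no fixed stop.
- The first such value has no 48-hour retest.
- Whoever programs the SAP 6.6.2 summary must choose a reading, and the count depends on the choice.

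**Working it through.** **Inputs.** The absolute limb of 8.0 g/dL, the 30% figure, and the 9.0 g/dL and 2 g/dL retest triggers are from Protocol 10.11. The 10.0 g/dL screening minimum is from Protocol 5.2. The documents give no distribution of baseline haemoglobin, so baselines *b* of 12 to 16 g/dL are illustrative assumptions. The plan states no derived figure to reproduce.

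**Reading 1: value below 30% of baseline.** The threshold is 0.30 × *b*. It exceeds 8.0 only if *b* > 8.0/0.30 = 26.7 g/dL, so the limb never adds a stop.

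**Reading 2: change of less than 30%.** From 15 to 14 g/dL is (15 − 14)/15 = 6.7%, which would count. At baseline 14, an unchanged value of 14.0 (0%) and a value of 10.0 (28.6%) both count, while 9.7 (30.7%) and 9.0 (35.7%) do not. The rule is inverted.

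**Reading 3: decrease of more than 30% (assumed intent).** The threshold is 0.70 × *b*. It adds to the 8.0 limb when *b* > 8.0/0.70 = 11.4 g/dL.

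| Baseline (g/dL) | 0.30 × *b* | 0.70 × *b* | Range with no fixed stop under reading 1 if reading 3 was meant | Part of that range at or above 9.0 |
|---|---|---|---|---|
| 10 | 3.0 | 7.0 | none | none |
| 12 | 3.6 | 8.4 | 8.0 to <8.4 | none |
| 13 | 3.9 | 9.1 | 8.0 to <9.1 | 9.0 to <9.1 |
| 14 | 4.2 | 9.8 | 8.0 to <9.8 | 9.0 to <9.8 |
| 15 | 4.5 | 10.5 | 8.0 to <10.5 | 9.0 to <10.5 |
| 16 | 4.8 | 11.2 | 8.0 to <11.2 | 9.0 to <11.2 |

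**What the monitoring retest covers.** Below 9.0 g/dL the prompt retest is unconditional. From 9.0 up it needs a fall of at least 2 g/dL and a value below the lower limit of normal. The part at or above 9.0 exists only when *b* > 9.0/0.70 = 12.9 g/dL. There a 30% fall is at least 0.30 × 12.9 = 3.9 g/dL, so the 2 g/dL condition is always met and the lower limit of normal decides. The documents do not give that limit. If it is at least 10.5 g/dL (assumption), the prompt retest covers the whole range at baseline 15.

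**Worked case.** Baseline 15 with two values of 9.5 g/dL is (15 − 9.5)/15 = 36.7%. Reading 3 requires a permanent stop. Reading 1 (threshold 4.5) and the 8.0 limb require neither a stop nor a 48-hour retest.

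**Two minor corrections found alongside, which carry no weight in the conclusion:**

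- Protocol 10.13.3.1, for public emergencies only, gives the home urine pregnancy kit a sensitivity of 25 IU/mL. The only other sensitivity figures, for serum tests in 8.2.8, are 25 mIU/mL; 8.2.8 gives none for urine tests. Since 25 IU/mL = 25,000 mIU/mL, the ratio is 25,000/25 = 1000, and a unit slip is probable.
- SAP 2.2 describes study drug as continuing during systemic rescue. Protocol 6.5.2 requires it to be held, and Protocol 10.12.2 requires permanent discontinuation after any rescue in the Czech Republic.

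**The case against.** The strongest reply is that nobody would adopt either literal reading. Beside an 8.0 g/dL limb and a list of toxicity thresholds, the only sensible meaning is more than 30% below baseline, and an investigator in doubt can ask the medical monitor.

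The consequence is also narrow. Haematology is drawn at every on-site visit (Schedule of Activities). Clinically significant abnormal values are to be repeated until they resolve (Protocol 8.2.5). Bleeding events, investigator judgement and prolonged withholding of drug each lead to permanent discontinuation. Unscheduled tests are available, and an external committee monitors safety. The protocol describes no specific haemoglobin signal; platelets are its only haematopoietic example. The 10.0 g/dL figure limits screening, not the Day 1 baseline.

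Most of this stands, and it limits the size of the problem. It does not remove it. None of these provisions fixes a stop or a 48-hour retest for a sustained fall of more than 30% that stays at or above 8.0 g/dL without bleeding. The medical-monitor clause concerns exceptions to stopping and does not supply the missing threshold. An intent that is easy to guess is still a guess, made separately at about 220 sites and again in the programming of the safety summary.

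**Conclusion.** The concern holds. The percent limb is wrong on both literal readings, and nothing in the protocol or SAP repairs it. On the assumption that a decrease of more than 30% was meant, the rule omits a fixed stop and the 48-hour retest for sustained values of, for example, 8.0 to <9.1 g/dL at baseline 13 and 8.0 to <10.5 g/dL at baseline 15. At baselines of 11.4 g/dL or below, the 8.0 limb governs and nothing is lost.

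The gap lies in the fixed stop and the speed of retest, not in detection. In SAP 6.6.2, coding the limb as a fraction of baseline adds nobody to the <8.0 g/dL cases, whereas the likely intent also counts sustained falls of more than 30%. The number of participants affected cannot be derived from the documents. Efficacy results, power and type I error are untouched. It should be corrected because it is a faulty threshold in a mandatory safety rule.

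**What to change.** Once the medical team confirms the intent, reword the Appendix 11 item as: *two sequential haemoglobin assessments <8.0 g/dL or a decrease of >30% from baseline*. Use the same definition for the SAP 6.6.2 summary.

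The minor corrections can go in at the same time:

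- In Protocol 10.13.3.1, change 25 IU/mL to 25 mIU/mL.
- In SAP 2.2, say that study drug is held during systemic rescue and may continue with topical rescue, except in the Czech Republic, where any rescue means permanent discontinuation.

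The cost is one protocol line, the matching SAP table definition and two one-line editorial changes. No visits, data or analyses are added.

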10.12. Appendix 12: Country-specific Requirements

10.12.1. France Contrat Unique

1. GCP Training

Before enrolling any participants, the investigator and any sub-investigators will complete the Pfizer-provided Good Clinical Practice training course (“Pfizer GCP Training”) or training deemed equivalent by Pfizer. Any investigators who later join the study will complete the Pfizer GCP Training or equivalent before performing study-related duties. For studies of applicable duration, the investigator and sub-investigators will complete Pfizer GCP Training or equivalent every 3 years during the term of the study, or more often if there are significant changes to the ICH GCP guidelines or course materials.

2. Study Intervention

No participants or third-party payers will be charged for study intervention.

3. SUSARs.

Pursuant to a sponsor’s safety reporting obligations under 21 CFR 312.32(c)(1), Pfizer will report to the Investigator all Serious Unexpected Suspected Adverse Reactions (“SUSARs”). Investigator will receive and review SUSAR reports and report SUSARs to the responsible IRB/IEC according to institution’s guidelines.

4. Collection of ethnic origin information

Information regarding ethnic origin will be collected in this study in compliance with the French Data Protection Authority, Commission nationale de l'informatique et des libertés (CNIL): Deliberation no. 2016-262 of 21 July 2016 amending the reference methodology for the processing of personal data conducted in connection with biomedical research (MR-001), §2.2.3 Nature of the data.

Individuals participating in this study will consent that this information can be collected in the study before they enter the study.

The electronic Case Report Form (eCRF) will be used as the source file for ethnic origin in France. This information will not be recorded in the participant’s medical records.

5. Termination Rights

Pfizer retains the right to discontinue development of abrocitinib at any time.+

